8.1.5. Primary Endpoints

Rate of all-cause mortality and major stroke within 12 months after surgery. All-cause mortality includes cardiac death, non-cardiac death, and death of unknown cause. Major stroke

is defined as a modified Rankin Scale (mRS) score ≥ 2 at 90 days after stroke onset (see Appendix 2).

Calculation formula: (Number of cases with all-cause mortality or major stroke at 12 months postoperatively / Total number of treated subjects) $\times 100\%$

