8.1.6. Secondary Efficacy Endpoint

- (1) Rate of immediate technical success following surgery. Immediate technical success is defined as successful delivery of the aortic and branching stent graft conveyors to their predetermined positions, accurate positioning and successful deployment of the stent, safe removal of the delivery device outside the body, and the absence of Type I and III endoleaks per imaging studies conducted at the end of the procedure with all branching stents patency.
- (2) Rate of aortic aneurysm progression under control. Maximum increase in the diameter of the aortic aneurysm was ≤ 5 mm when compared with preoperative aortic aneurysm as of a 12-month postoperative CTA review.
- (3) Incidence of Type I or Type III endoleaks. Intraoperative, 1-month, 6-month, and 12-month DSA or CTA imaging studies showing endoleaks. Intraoperative endoleaks subject to adjuvant treatment are not recorded. Endoleaks occurring after the completion of the procedure followed by one or more endoleaks occurring in the same subject at different follow-up stages that were not treated are counted as a single instance.
- (4) Incidence of aortic covered stent graft displacement. CTA examination will be performed at 1, 6, and 12 months post operation to determine if the stent has migrated, and evaluations will be recorded for both the main and branch stents. Displacement is defined as a displacement of more than 10 mm in the aortic and branch stent grafts at follow-up time points compared with the 30-day postoperative reference imaging.
- (5) Postoperative branch vessel patency rate. CTA examinations will be performed at 1, 6, and 12 months post-operation to evaluate branch vessel reconstruction and assess for occlusion, stenosis, or in-stent thrombosis.

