8.2.2. Trial Conduct

1) Visit 1: Screening Period (Day -15 to 0)

After the subject signs the informed consent form, baseline information and baseline examinations shall be collected, and screening shall be performed according to the inclusion and exclusion criteria. Eligible screened subjects will complete enrollment registration. The specific collected items are as follows:

- Demographic information, including age, gender, height, weight
- Physical examination data, including heart rate, respiration, blood pressure and body temperature
- Family history and previous medical history, including surgical history, concomitant diseases, concomitant medications and medical treatments
- Routine laboratory testing:
 - o Blood panel: Erythrocytes, leukocytes, platelet count and hemoglobin

- o Urine panel: pH, leukocytes, erythrocytes and proteins
- o Liver and kidney function: Creatinine, alanine aminotransferase (ALT), aspartate aminotransferase (AST), total bilirubin (TBIL) and direct bilirubin (DBIL)
- o Coagulation function: Activated partial thromboplastin time (APTT), prothrombin time (PT), internationalized standard ratio (INR), fibrinogen (FIB), thromboplastin time (TT) and D-dimer
- Pregnancy test (for female patients of childbearing age)
- Clinical Symptom Assessment (Modified Rankin Scale, mRS)
- 12-Lead ECG
- CTA angiography
- Cerebral CTA or MRA
- Echocardiography examination
- Concomitant medications

2) Visit 2: Intraoperative (0 day)

Record the procedural details; the specific collected items are as follows:

- Physical examination data
- DSA imaging data
- Surgery-related records (selection of stent type, arterial access, deployment, Interventional operation time (the time the sheath enters the body to the time the sheath is pulled out of the body), immediate success, etc.)
- Concomitant medications
- Adverse events
- Device defects

3) Visit 3: Before discharge

- Physical examination
- Blood panel: Erythrocytes, leukocytes, platelet count and hemoglobin
- Urine panel: pH, leukocytes, erythrocytes and proteins
- Liver and kidney function: Creatinine, alanine aminotransferase (ALT), aspartate

aminotransferase (AST), total bilirubin (TBIL) and direct bilirubin (DBIL)

- Coagulation function: Activated partial thromboplastin time (APTT), prothrombin time (PT), internationalized standard ratio (INR), fibrinogen (FIB), thromboplastin time (TT) and D-dimer
- Clinical Symptom Assessment (Modified Rankin Scale, mRS)
- 12-Lead ECG

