9.2. Analysis Sets

The trial's statistical analysis will be conducted on the basis of the following analyzed populations,

which need to be clearly defined before the statistical analysis begins, and in this trial they include:

1. Full Analysis Set (FAS): Refers to the subject set that is as close as possible to intention-to-treat (ITT) principles, which is derived from all randomized subjects with minimal and reasonable censoring, and contains all subjects who have been subject to randomization and have previously used an investigational device. The FAS will be used for the evaluation of primary and secondary indicators.

2. Per Protocol Set (PPS): All patients showing good compliance with the trial protocol, good adherence, completion of the treatment specified in the trial protocol and no deficiencies in key efficacy indicators. The PPS will be used for the evaluation of primary and secondary indicators.

3. Safety Set (SS): All subjects who used an investigational device following randomization and underwent a safety evaluation. The SS will be is used for an analysis of safety indices.

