9.3. Elimination Criteria

Prior to the statistical analysis of data, the principal investigator, sponsor, and statistical analysis institution shall assess whether an individual subject meets any of the following conditions. The principal investigator shall comprehensively determine whether to eliminate the subject from the analysis sets based on factors including the subject's completion of the trial, reasons for trial, and shall issue a relevant written explanation for the elimination. A subject shall be considered for elimination if any of the following criteria is met:

- 1) The subject was enrolled in violation of the inclusion/exclusion criteria and should not have been admitted to the trial.
- 2) During the trial, the investigator determined that the subject had other factors precluding continued trial participation, and the subject's trial participation was formally terminated.
- 3) Major protocol deviations occurred during the implementation of the clinical trial protocol, including subjects whose treatment regimen were modified during the trial.
- 4) The subject failed to comply with the trial plan with poor compliance, which has impaired the efficacy or safety evaluation. Examples include: never used the investigational medical device, failure to collect data required for efficacy and safety evaluation in accordance with the trial protocol, and absence of any observation data.

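### No analysis set counts a procedure that was started but abandoned before the device was used: this inflates technical success and can bias the event rates either way

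*Protocol*

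**What the plan says.** **Enrolment.** Section 8.2.2 (Visit 1, screening) has registration before surgery: "Eligible screened subjects will complete enrollment registration". Section 8.2 lists enrolment before product selection and surgery.

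**Full Analysis Set.** Section 9.2 gives the principle first: "Refers to the subject set that is as close as possible to intention-to-treat (ITT) principles". The membership rule follows: the set "contains all subjects who have been subject to randomization and have previously used an investigational device". On its role: "The FAS will be used for the evaluation of primary and secondary indicators".

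**Safety Set.** Section 9.2: "All subjects who used an investigational device following randomization and underwent a safety evaluation". Section 9.4.2 makes this the main set for the secondary safety endpoints.

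**Per Protocol Set.** It is narrower, since it requires completed treatment.

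**Primary denominator.** The formula in section 8.1.5 divides by "Total number of treated subjects".

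**Elimination.** Section 9.3, criterion (4), concerns poor compliance that has impaired evaluation, and illustrates it so: "Examples include: never used the investigational medical device, failure to collect data required for efficacy and safety evaluation".

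**Technical success.** Section 8.1.6 (1): "Immediate technical success is defined as successful delivery of the aortic and branching stent graft conveyors to their predetermined positions". Accurate deployment, safe removal, absence of Type I and III endoleak and branch patency are required as well.

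**The concern.** Whether a device is used is settled during the operation and depends on how the operation goes. Suppose vascular access or wire passage fails, or the subject has a stroke or dies after the procedure has begun but before any component is introduced. That subject is enrolled and has been exposed to the procedure, but meets neither the FAS nor the Safety Set condition. Section 9.3 adds to the difficulty by describing non-use as a compliance problem, when it may be a procedural outcome.

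The trial is a single-arm comparison with a fixed performance criterion (section 8.1.2), so no control arm loses subjects in the same way. Technical success then describes those who got as far as device use, not those for whom the operation was undertaken. The primary and 30-day rates lose the abandoned cases too, including any abandoned because of, or followed by, death or stroke.

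**Working it through.** **1. The base of 90.** Section 8.1.4.8 gives 72 valid cases and 20% dropout: 72 / (1 − 0.20) = 90. The plan's figure reproduces. The performance criterion and the expected rate are not shown in the public document, so the 72 cannot be checked.

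**2. Where an abandoned case goes.** Take a subject who is enrolled, whose procedure is started, and in whom no component is introduced.

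- FAS: device use is required, so the subject is out.
- Safety Set: device use is required, so out.
- Per Protocol Set: completed treatment is required, so out.
- Missing-data rules in section 9.5: these impute within the FAS and Per Protocol Set, so they do not bring the subject back.
- Section 8.1.4.3 keeps source data on all enrolled subjects for an intention-to-treat analysis, but section 9.2 defines no set that would use them.

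**3. Technical success.** Let N be the procedures started, k those abandoned before device use, and f the failures among the rest. As written the rate is (N − k − f)/(N − k). With all started procedures counted it is (N − k − f)/N. The numerators are equal and the first denominator is smaller, so the rate as written is higher whenever k is above 0 and there is any success. Assumed: N = 90, f = 4.

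| k | As written | All started |
|---|---|---|
| 1 | 85/89 = 95.5% | 85/90 = 94.4% |
| 3 | 83/87 = 95.4% | 83/90 = 92.2% |
| 5 | 81/85 = 95.3% | 81/90 = 90.0% |

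The rate as written hardly changes with k. The rate over all started procedures falls by about 1.1 points per abandoned case (1/90).

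**4. Primary rate.** Assumed: 15 events among 87 device-used subjects and k = 3. As written: 15/87 = 17.2%. With all 90 counted:

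| Events among the 3 | All started | Effect of the exclusion |
|---|---|---|
| 0 | 15/90 = 16.7% | raises the reported rate |
| 1 | 16/90 = 17.8% | lowers it |
| 2 | 17/90 = 18.9% | lowers it |
| 3 | 18/90 = 20.0% | lowers it |

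The exclusion lowers the reported rate only if the event proportion among the abandoned cases exceeds that among the device-used cases.

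**5. The quantity that decides the trial.** Section 9.4.2 compares the upper 95% limit with the performance criterion. In a second illustration, with 9 events among 87 used and k = 3 (Clopper-Pearson limits), the upper limit as written is 18.7% (9/87 = 10.3%). With all 90 counted it runs from 18.1% (9/90 = 10.0%) to 22.1% (12/90 = 13.3%).

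**The case against.** **A device-used denominator is a legitimate choice.** It is common in device safety analysis, and section 8.1.5 fixes treated subjects in advance. This stands in part. Such a set is acceptable as a supplementary set. Here it is the broadest set in the plan, and it is labelled close to intention-to-treat.

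**A reader might infer that every delivery failure is lost.** The text does not support this. *Used* is undefined, and if introducing a delivery system counts as use, failed delivery, positioning or deployment stays in the FAS as technical failure. On that reading only earlier abandonment is lost. The open definition is still a fault. Section 7.3 (2) describes a typical procedure with five grafts (one ascending, one arch, three branch), so *used* could mean introduced, deployed or fully implanted.

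**A reader might infer that the exclusion can only lower the death and stroke rates.** It cannot be put that way: 15/87 = 17.2% exceeds 15/90 = 16.7% when the three excluded subjects are event-free.

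**A reader might infer that section 9.3 removes non-users automatically.** It says only that they are considered for elimination, with the principal investigator deciding and explaining in writing. The gap comes from the definitions in section 9.2; section 9.3 only reinforces it.

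**The events are recorded anyway.** Adverse events are collected from the day of surgery, and section 9.4.2 provides for a list of non-completers with reasons and a list of adverse events. This is true, but a listing does not put the subjects into the rates.

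**Abandonment may be rare.** Suitable arterial access is an inclusion criterion, and the lead site must confirm the CTA measurements before enrolment (section 8.2.1). This is fair, and nothing in the protocol points to a particular number.

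**Conclusion.** The point holds. Section 9.2 states a principle close to intention-to-treat and then a membership rule that leaves started but abandoned procedures in no analysis set. For technical success the error always favours the device, by about one percentage point per abandoned case in 90. For the primary and 30-day rates the direction is open; the worry is abandonment caused or followed by death or stroke.

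The sizes rest on assumed counts: 1 to 5 abandoned procedures, 4 other technical failures, and 15 or 9 primary events. The performance criterion is not shown, so no effect on the trial's conclusion can be demonstrated. The definitions should be corrected before data are analysed, but this is not evidence that the result will be wrong.

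**What to change.** - **Main set.** Define the FAS and the section 8.1.5 denominator as all enrolled subjects in whom the index procedure was started. Take the start as the beginning of anaesthesia or the first attempt at arterial access, whichever comes first, whether or not access succeeded or a device was introduced. A trigger of access *obtained* would still drop failed access.
- **Safety.** Use the same set for the main safety rates. Keep a device-used set as supplementary, with *used* defined, for example as delivery system introduced.
- **Counting.** Count abandonment after procedure start as technical failure. Count deaths and strokes from procedure start in the primary and 30-day endpoints.
- **Section 9.3 (4).** Remove non-use from the compliance examples for started procedures.
- **Randomization.** Delete this condition from the FAS and Safety Set definitions in the same edit. The trial is single-arm, so the sentences need rewriting in any case.

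The cost is wording in sections 8.1.5, 8.1.6, 9.2 and 9.3, with no extra patients or visits. Visit 2 already records arterial access, procedural details and adverse events. The small downside is that reported rates may be slightly less favourable.

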9.3. Elimination Criteria

Prior to the statistical analysis of data, the principal investigator, sponsor, and statistical analysis institution shall assess whether an individual subject meets any of the following conditions. The principal investigator shall comprehensively determine whether to eliminate the subject from the analysis sets based on factors including the subject's completion of the trial, reasons for trial, and shall issue a relevant written explanation for the elimination. A subject shall be considered for elimination if any of the following criteria is met:

- 1) The subject was enrolled in violation of the inclusion/exclusion criteria and should not have been admitted to the trial.
- 2) During the trial, the investigator determined that the subject had other factors precluding continued trial participation, and the subject's trial participation was formally terminated.
- 3) Major protocol deviations occurred during the implementation of the clinical trial protocol, including subjects whose treatment regimen were modified during the trial.
- 4) The subject failed to comply with the trial plan with poor compliance, which has impaired the efficacy or safety evaluation. Examples include: never used the investigational medical device, failure to collect data required for efficacy and safety evaluation in accordance with the trial protocol, and absence of any observation data.

9.4. Statistical Design, Methodology and Analytical Procedures

9.4.1. Statistical Design

This clinical trial adopts a prospective, multi-center, superiority, randomized controlled trial design to evaluate the efficacy and safety of the investigational device.

9.4.2. Statistical Methodology and Analysis

1) General Principles

For quantitative variables, mean, standard deviation, median, minimum, maximum, lower quartile (Q1), and upper quartile (Q3) will be calculated. For categorical variables, the number and percentage of subjects in each category will be presented.

Comparison of general characteristics between the two groups will be analyzed using appropriate methods according to the type of variables. Between-group comparisons of quantitative data will be performed using the independent samples t-test (for homogeneous variance and normal distribution) or the Wilcoxon rank-sum test, depending on the data distribution. Categorical data will be analyzed using the chi-square test or Fisher's exact test (if the chi-square test is not applicable). Ordinal data will be analyzed using the Wilcoxon rank-sum test or the CMH test.

2) Completion Status and Demographic Analysis

The number of enrollments and completions for each center will be summarized and a list of fallout cases as well as a detailed list of reasons for non-completion will be created. Patients' demographic characteristics (age, sex, etc.), relevant medical history treatment, etc. will be described. A demographic analysis will be performed based on an FAS analysis set.

3) Primary Endpoints

Primary Endpoint: The incidence of all-cause death or major stroke within 12 months after the procedure. All-cause death includes cardiac death, non-cardiac death, and death of unknown cause. Major stroke is defined as a modified Rankin Scale (mRS) score ≥ 2 assessed at 90 days after stroke onset. The hypothesis testing is specified as follows:

Null Hypothesis: $H_0: P_T - P_C \leq \Delta$

Alternative Hypothesis: $H_1: P_T - P_C > \Delta$

$\alpha = 0.025$ (single tail)

At the significance level of $\alpha = 0.025$ (one-sided) and statistical power of $1 - \beta = 0.8$, the incidence rate of all-cause mortality or major stroke within 12 months post-procedure shall be statistically described, and its two-sided 95% confidence interval (95% CI) shall be estimated. The upper limit of the 95% CI

shall be compared with the Objective Performance Criteria (OPC). Statistical conclusions will then be drawn accordingly. If the upper limit of the 95% CI is lower than the objective performance criterion P_0 , the primary endpoint shall meet the trial requirements, and the investigational device can be considered to satisfy the requirements for clinical application.

4) Secondary Endpoints

Technical success immediately post-procedure, aortic aneurysm progression control rate, incidence of Type I or Type III endoleak, incidence of aortic stent graft migration, postoperative patency rate of branch vessels, incidence of conversion to open thoracic surgery or secondary interventional procedure, major adverse event rate within 30 days post-operation, aortic aneurysm-related mortality at 12 months post-operation, incidence of serious adverse events, and incidence of device-related adverse events.

Statistical description shall be performed for secondary efficacy indicators, with frequencies and percentages calculated. FAS (Full Analysis Set) and PPS (Per Protocol Set) analyses shall also be conducted.

Statistical description shall be performed for secondary safety indicators, with frequencies and percentages calculated. The SS (Safety Set) analysis shall be adopted as the primary approach.

The Kaplan-Meier method shall be used to estimate the survival rate and its 95% confidence interval, with Kaplan-Meier curves plotted accordingly.

Descriptive statistical analysis shall be performed for the changes of all laboratory parameters before and after the trial. All adverse events occurring during the trial shall be recorded in detail; descriptive statistical analysis of adverse events shall be conducted with a list attached.

In addition to the above statistical methods, detailed and additional exploratory analyses may be required, which shall be confirmed in the Study Report and Statistical Analysis Plan (SAP)..

9.5. Statistical methods for all data, including the handling of missing, unused or erroneous data (including premature discontinuation and withdrawal) and inconsistent data.

A Statistical Analysis Plan (SAP) shall be developed prior to study initiation. After database lock, statistical analysis shall be performed in accordance with the SAP, and a statistical analysis report shall be generated based on the results.

(1) Handling of missing data: Missing data shall be handled according to the analysis set in which they are included. Missing data for the primary endpoint in the Full Analysis Set (FAS) shall be classified by reason as follows:

Missing data clearly due to unsatisfactory efficacy: loss to follow-up or missing primary efficacy data resulting from adverse events, death, etc., related (or possibly related) to the investigational device or aortic dissection.

Missing data not attributable to unsatisfactory efficacy: loss to follow-up, failure to complete assessments, or other reasons such as force majeure (e.g., epidemic restrictions) resulting from adverse events, death, etc., unrelated to the investigational device or aortic dissection.

For the first category of missing data, worst-case imputation shall be used in both the FAS and Per Protocol Set (PPS), treated as “12-month postoperative failure”. For the second category of missing data, three imputation methods shall be applied separately, followed by sensitivity analysis:

1) Best-case imputation: all treated as “12-month postoperative success”; 2) Worst-case imputation: all treated as “12-month postoperative failure”; 3) Tipping-point analysis: the imputation proportions of success and failure in the two groups shall be varied iteratively to comprehensively demonstrate whether the study meets the statistical hypothesis under different scenarios and to identify the tipping point at which the conclusion changes.

No statistical imputation shall be used for missing data of other endpoints.

(2) Handling of inconsistent data: During data management, logical checks shall be performed on the database. Inconsistent data shall be queried via data query forms sent to investigators. Inconsistent data shall be resolved based on written responses from investigators. The database shall not be locked until all inconsistent data has been resolved.

(3) Handling of erroneous data: During data management, quality control should be conducted on the database. Erroneous data shall be identified and queried via data queries (Query). Errors shall be corrected based on investigators' responses, and queries shall be closed only after confirmation from investigators. The database shall not be locked until all erroneous data has been corrected.

